### 6.2.3. Study Day and Reference Dates

The study reference date is the study treatment start date and will be used to calculate study day for safety and efficacy measures.

The study day is calculated as below:

- Assessment Date = Missing → Study Day = Missing
- Assessment Date < Reference Date → Study Day = Assessment Date – Ref Date
- Assessment Date ≥ Reference Date → Study Day = Assessment Date – Ref Date + 1

### 6.2.4. Assessment Windows for Early Termination

Unless otherwise specified, unscheduled visits will not be mapped to a visit window, and will be listed only.

Assessment for Early Termination visits are as follows:

Analysis Set / Domain	Parameter (if applicable)	Target	Analysis Window		Analysis Timepoint
			Beginning Timepoint (Days)	Ending Timepoint (Days)	
Lab/Vital Signs	Numeric parameters	1	1	2	Week 1 Day 1
		4	3	6	Week 1 Day 4
		8	7	9	Week 2 Day 8
		11	10	12	Week 2 Day 11
		15	13	18	Week 3 Day 15
		22	19	25	Week 4
		1+7(x-1)	1+7(x-1)-3	1+7(x-1)+3	Week x
		85	82	88	OT-Week 1
		92	89	95	OT-Week 2
		106	96	119	OT-Week 4
		134	120	147	OT-Week 8
		162	148	175	OT-Week 12
		190	176	203	OT-Week 16
		218	204	231	OT-Week 20
		246	232	246	OT-Week 24

#### 6.2.5. Assessment Windows for Analyses and Multiple Measurements at One Analysis Timepoint

The primary endpoint is defined as “Achieving serum HBsAg level <LLOQ at any time point up to and including Week 12 without the use of PEG-interferon or other immunomodulator therapies”. No analysis window will be assigned and all values up to Week 12, including unscheduled visit results, will be considered. The upper bound of the analysis date is defined as:

Target day of the Week 12 visit (78) + 3 days

Note: 3 days as allowed for the Week 12 dosing.

For secondary endpoints:

- sustained Virologic Response (HBsAg <LLOQ and HBV DNA <LLOQ)
- sustained HBsAg Response (HBsAg <LLOQ) for 24 weeks

after the planned end of GSK3228836 treatment (all values including unscheduled visit results will be considered):

	Parameter (if applicable)	Target Study Day	Analysis Window		Analysis Timepoint	Protocol Visit
			Beginning Timepoint	Ending Timepoint		
Efficacy	HBsAg and HBV DNA; or HBsAg	78	64	98	End of '836 Treatment – Planned	Week 12
		134	99	154	Post '836 treatment Week 8 – Planned	Week 20
		190	155	210	Post '836 treatment Week 16 – Planned	Week 28
		246	211	266	Post '836 treatment Week 24 – Planned	Week 36

For secondary endpoints:

- sustained Virologic Response(HBsAg <LLOQ and HBV DNA<LLOQ)
- sustained HBsAg Response(HBsAg <LLOQ) 24 weeks

after the actual end of GSK3228836 treatment (all values including unscheduled visit results will be considered):

	Parameter (if applicable)	Target Study Day	Analysis Window		Analysis Timepoint	Protocol Visit
			Beginning Timepoint	Ending Timepoint		
Efficacy	HBsAg and HBV DNA; or HBsAg	X = Target study day of the last treatment dose	Max (X-14, 1)	X+20	End of '836 Treatment - Actual	-
		X + 56	X+21	X + 76	Post '836 treatment Week 8 - Actual	-
		X + 112	X+ 77	X + 132	Post '836 treatment	-

	Parameter (if applicable)	Target Study Day	Analysis Window		Analysis Timepoint	Protocol Visit
			Beginning Timepoint	Ending Timepoint		
					Week 16 - Actual	
		X + 168	X + 133	X + 188	Post '836 treatment Week 24 - Actual	-

1. For example, if the subject received the last treatment dosing at the W2/D8 visit, then the target day is 8; if the subject received the last treatment dosing at the W2/D11 visit (loading schedule), then the target day is 11; if the subject received the last treatment dosing at the W9/D57 visit, then the target day is 57.

For the End of '836 Treatment Analysis Timepoint, if there are multiple values within an analysis window the following rules will be applied:

1. The latest available assessment in the window will be selected.

For Post '836 Treatment Analysis Timepoints, if there are multiple values within an analysis window the following rules will be applied:

1. Worst non-missing value in the analysis window will be selected, if values are the same then the value closest to target day will be selected. If there are multiple values equidistant from the target day, the earliest will be selected. If all values within an analysis window are missing, then the result is missing for the analysis window.
2. Worst value is defined in the order of: highest actual value, then <LLOQ, and then TND.

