7.2. Participant Discontinuation/Withdrawal from the Study

- A participant may withdraw from the study at any time at his/her own request or may be withdrawn at any time at the discretion of the investigator for safety, behavioral, compliance or administrative reasons.
- The investigator may ask participants to withdraw from study treatment but continue with visits instead of withdrawing completely from the study.
- At the time of discontinuing from the study, if possible, an early termination visit should be conducted, as shown in the SoA (see Section 1.3). See SoA for data to be collected at the time of study discontinuation and follow-up and for any further evaluations that need to be completed.
- The participant will be permanently discontinued both from the study intervention and from the study at that time.
- If the participant withdraws consent for disclosure of future information, the sponsor may retain and continue to use any data collected before such a withdrawal of consent.
- If a participant withdraws from the study, he/she may request destruction of any samples taken and not tested, and the investigator must document this in the site study records.

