9.4.4. Secondary Endpoint(s)

Estimands supporting the secondary objective of assessing sustainability of serum HBsAg loss by GSK3228836 for up to 24 weeks off-treatment are defined as follows:

- The group of estimands supporting this objective in participants with CHB receiving 300 mg GSK3228836 for 12 weeks (with at least one dose of IP) is the percentage of participants for each variable regardless of completing IP, interruptions in IP or adherence to IP, without the use of PEG-interferon or other immunomodulator therapies. If PEG-interferon or other immunomodulator therapies are used then the participant's outcome will be treated as a failure.
- Variables:
 - Sustained HBsAg Response (HBsAg <LLOQ) for 24 weeks after the planned end of GSK3228836 treatment without the use of PEG-interferon or other immunomodulator therapies
 - HBsAg from Week 13 to Week 36 will be used to assess sustained HBsAg response after the planned end of GSK3228836 treatment.
 - Sustained HBsAg Response (HBsAg <LLOQ) for 24 weeks after the actual end of GSK3228836 treatment without the use of PEG-interferon or other immunomodulator therapies
 - HBsAg for 24 weeks after end of actual treatment will also be used to assess sustained HBsAg response after the actual end of GSK3228836 treatment.
- Population Summary: percentage of participants for each variable.
- Analysis windows for the post GSK3228836 treatment assessments will be defined in the analysis plan.

Estimands supporting the secondary objective of assessing sustainability of serum HBsAg and HBV DNA (Sustained Virologic Response) loss by GSK3228836 for up to 24 weeks off treatment are defined as follows:

- The group of estimands supporting this objective in participants with CHB receiving 300 mg GSK3228836 for 12 weeks (with at least one dose of IP) is the percentage of participants for each variable regardless of completing IP, interruptions in IP or adherence to IP, without the use of PEG-interferon or other immunomodulator therapies. If PEG-interferon or other immunomodulator therapies are used then the participant's outcome will be treated as a failure.
- Variables:
 - Sustained Virologic Response (HBsAg <LLOQ and HBV DNA <LLOQ) for 24 weeks after the planned end of GSK3228836 treatment

- HBsAg and HBV DNA from Week 13 to Week 36 will be used to assess sustained virologic response after the planned end of GSK3228836 treatment without the use of PEG-interferon or other immunomodulator therapies.

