### ***Main analytical approach***

Percentages will be summarised and presented for:

- Sustainability of Serum HBsAg loss

Analysis windows for the post GSK3228836 treatment assessments are defined in Section [6.2.5](#).

If all analysis windows have non-missing response information, a participant's response (Responder or Non-responder) for sustained HBsAg response after the planned end of GSK3228836 treatment is determined as follows:

- If participant took PEG-interferon or other immunomodulator therapies during 12 week treatment period or 24 week follow-up period then participant is Non-Responder
- Else if participant had sustained HBsAg response (HBsAg <LLOQ) for 24 weeks after planned end of GSK3228836 treatment then participant is a Responder.
- Otherwise participant is Non-Responder.

If all analysis windows have non-missing response information, a participant's response (Responder or Non-responder) for sustained HBsAg response after the actual end of GSK3228836 treatment is determined as follows:

- If participant took PEG-interferon or other immunomodulator therapies during 24 week follow-up period then participant is Non-Responder
- Else if participant had sustained HBsAg response (HBsAg <LLOQ) for 24 weeks after actual end of GSK3228836 treatment then participant is a Responder.
- Otherwise participant is Non-Responder.

For participants where sustained HBsAg response in the absence of PEG-interferon or other immunomodulator therapies cannot be ascertained due to missing data (withdrawal from the study or missing due to other reasons), the participant will be assumed not to have achieved SVR (non-responder imputation).

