##### ***Main analytical approach***

Percentages will be summarised and presented for:

- Sustainability of Serum HBsAg and HBV DNA loss (Sustained Virologic Response).

Analysis windows for the post GSK3228836 treatment assessments are defined in Section [6.2.5](#).

If all analysis windows have non-missing response information, a participant's response (Responder or Non-responder) for sustained virologic response after the planned end of GSK3228836 treatment is determined as follows:

- If participant took PEG-interferon or other immunomodulator therapies during 12 week treatment period or 24 week follow-up period then participant is Non-Responder
- Else if participant had sustained virologic response (HBsAg <LLOQ and HBV DNA <LLOQ) for 24 weeks after planned end of GSK3228836 treatment then participant is a Responder.
- Otherwise participant is Non-Responder.

If all analysis windows have non-missing response information, a participant's response (Responder or Non-responder) for sustained virologic response after the actual end of GSK3228836 treatment is determined as follows:

- If participant took PEG-interferon or other immunomodulator therapies during 12 week treatment period or 24 week follow-up period then participant is Non-Responder
- Else if participant had sustained virologic response (HBsAg <LLOQ and HBV DNA <LLOQ) for 24 weeks after actual end of GSK3228836 treatment then participant is a Responder.
- Otherwise participant is Non-Responder.

For participants where sustained virologic response in the absence of PEG-interferon or other immunomodulator therapies cannot be ascertained due to missing data (withdrawal from the study or missing due to other reasons), the participant will be assumed not to have achieved SVR (non-responder imputation).

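### A Week 32 sample alone can fill the post-treatment Week 24 window, so a participant last seen 20 weeks off treatment can be counted as a 24-week sustained responder

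*SAP*

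**What the plan says.** Protocol 9.4.4 defines the planned-end variable by the follow-up period: "HBsAg from Week 13 to Week 36 will be used to assess sustained HBsAg response after the planned end of GSK3228836 treatment". The sustained virologic response variable covers the same weeks and adds HBV DNA.

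SAP 6.2.5 turns this into four windows. The last, "Post '836 treatment Week 24 – Planned", has target Day 246, protocol visit Week 36, and bounds Day 211 to Day 266. The actual-end table uses X+133 to X+188 with target X+168, where "X = Target study day of the last treatment dose". Both tables accept scheduled and unscheduled values. In post-treatment windows the worst non-missing value is taken, and "If all values within an analysis window are missing, then the result is missing for the analysis window".

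The main analytical approach in SAP 4.3.1.1 and 4.3.1.2 opens with the condition "If all analysis windows have non-missing response information" and then classifies the participant as responder or non-responder. Non-responder imputation is kept for participants whose sustained response "cannot be ascertained due to missing data (withdrawal from the study or missing due to other reasons").

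**The concern.** The window meant to represent 24 weeks off treatment contains two scheduled visits, Week 32 and Week 36, and either one fills it. No rule requires a sample near Week 36. A participant who leaves after Week 32 is exactly the case that the imputation sentence has in mind when it names study withdrawal, yet the window logic never reaches that sentence.

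Worst-value selection protects against ignoring a late relapse that was measured. It does nothing when the late sample was never taken. The early termination visit is not a reliable backstop: Protocol 7.2 says "At the time of discontinuing from the study, if possible, an early termination visit should be conducted", and such a visit on Days 211 to 231 would itself fill the window.

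The objective is durability for up to 24 weeks off treatment, so the last four weeks are part of what is being claimed.

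**Working it through.** **Inputs.** Visit days and the ± 3-day follow-up window: Protocol 1.3, Table 4 (Week 28 = Day 190, Week 32 = Day 218, Week 36 = Day 246). Last planned dose: Day 78 (Table 3). Windows and selection rules: SAP 6.2.5. Classification: SAP 4.3.1.1 and 4.3.1.2. Sample size: about 20, at most 24 (SAP 5).

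**Reproducing the SAP's windows.** Putting X = 78 into the actual-end formulas gives 64–98, 99–154, 155–210 and 211–266. These match the planned table, and 78 + 168 = 246 matches its target.

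**What falls in the last window (planned).** Week 32 spans 218 − 3 = 215 to 218 + 3 = 221, wholly inside 211–266.

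- Week 32: (218 − 78)/7 = 140/7 = 20.0 weeks after the last dose.
- Week 36: (246 − 78)/7 = 168/7 = 24.0 weeks.
- Shortfall: 246 − 218 = 28 days.
- Earliest value that can fill the window, for example an unscheduled sample on Day 211: (211 − 78)/7 = 19.0 weeks.

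**Applying the rules as written**, with every other sample below LLOQ and no prohibited therapy:

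| Week 32 | Week 36 | Last window | Class |
|---|---|---|---|
| <LLOQ | absent | filled | Responder |
| <LLOQ | detectable | filled, worst value detectable | Non-responder |
| absent | absent | missing | Non-responder |

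The first row is the problem.

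**Actual-end table.** For last doses on Days 64, 71 and 78, both Week 32 and Week 36 lie in the window, and Week 32 is 22.0, 21.0 and 20.0 weeks after the last dose. For last doses on Day 57 or earlier, Week 36 is outside the window, but an earlier visit can still fill it alone. The SAP's footnote gives such a case: "if the subject received the last treatment dosing at the W9/D57 visit, then the target day is 57". The window is then 57 + 133 = 190 to 57 + 188 = 245. A Week 28 sample on Day 190 is 133/7 = 19.0 weeks after the last dose, 168 − 133 = 35 days short. This needs Week 32 to be missing too, and the Week 28 sample to fall on Day 190 or later.

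**Comparison with SAP 6.2.4.** The early-termination mapping labels Days 204–231 as off-treatment Week 20 and starts off-treatment Week 24 at Day 232, which is (232 − 78)/7 = 22.0 weeks. Day 218 is thus off-treatment Week 20 in one table and able to stand for Week 24 in the next.

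**Effect on the reported percentage.** One participant is 1/20 = 5.0 points, or 1/24 = 4.2 points; two would be 10.0 or 8.3.

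**The case against.** The best counter-argument is that the SAP does not literally say that four filled windows below LLOQ make a responder. Filled windows are only the entry condition. The responder step separately asks for a response lasting 24 weeks, and the imputation sentence covers a response that cannot be established. A careful statistician could use either sentence to class someone last seen at 20 weeks as a non-responder. That reading is possible, but the only working definition of missing data for this endpoint is at window level. Programming to the text gives Responder, and if two programmers can reach different counts the rule needs changing anyway.

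Second, the protocol leaves the windows to the analysis plan, and including Week 32 has a conservative purpose because a relapse there counts against the participant. Both points are true. Neither makes 20 weeks of observation meet a 24-week variable, and the proposed change keeps the Week 32 value in the worst-value selection.

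Third, 6.2.4 serves early-termination mapping of laboratory and vital-sign data and does not govern this endpoint. That stands: the difference in labels supports the point but is not a contradiction that decides it.

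Fourth, the number affected is unknown. Sites are asked to reschedule missed visits, HBsAg and HBV DNA are sampled at early termination, and the endpoints have no test or decision rule attached. This also stands, and it limits the importance of the point.

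**Conclusion.** The concern holds. As written, the rules class a participant with no sample after Week 32 as a 24-week sustained responder, for both sustained HBsAg response and sustained virologic response. For a last dose on Day 78 with visits on their nominal days, the observation is 28 days short. In the Day 57 example it can be 35 days short under the conditions given above.

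Compared with the non-responder imputation the SAP intends for missing data, the error can only raise the rate, by 5.0 points per participant at N=20 or 4.2 at N=24. The conclusion assumes that missingness is judged window by window, which is the only operational rule given. The documents state no rate of participants seen at Week 32 but not at Week 36, so the total effect cannot be calculated.

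The primary endpoint, with its upper bound at Day 81, is unaffected. In an exploratory single-arm study with descriptive secondary endpoints, this should be corrected but does not threaten the main result.

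**What to change.** Add one rule to each table in SAP 6.2.5. The post-treatment Week 24 window counts as non-missing only if an HBsAg result (for sustained virologic response, also an HBV DNA result) exists on or after Day 232 in the planned table, or X+154 in the actual table. Otherwise, apply the non-responder imputation already stated in 4.3.1.1 and 4.3.1.2. Keep worst-value selection over the full existing window, so that a relapse at Week 32 still counts.

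Day 232 is the lower bound of off-treatment Week 24 in SAP 6.2.4, and 78 + 154 = 232 carries it to the actual table. It allows 246 − 232 = 14 days before target, so the minimum is 22.0 weeks. The tolerance is a choice. For a last dose on Day 64, a Week 32 sample on Day 218 is exactly X+154 and would still suffice.

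The rule does not penalise complete follow-up. For each of the 14 scheduled dosing days, X+154 to X+188 contains at least one whole ± 3-day visit window:

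- last dose Day 1 or 4: Day 162
- last dose Days 8 to 29: Day 190
- last dose Days 36 to 57: Day 218
- last dose Days 64 to 78: Day 246

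The cost is one sentence per table and minor reprogramming. A true sustained responder who misses the late sample would be counted as a failure, so the reported rate may be slightly lower; that is consistent with the SAP's stated handling of missing data.

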8.1. Efficacy Assessments

The primary objective measurement for efficacy in this study is the assessment of 12 weeks of GSK3228836 treatment on serum HBsAg levels in participants with CHB. The primary efficacy endpoint is achieving serum HBsAg level <LLOQ by Week 12.

Any HBsAg greater than LLOQ after achieving HBsAg seroclearance needs to be confirmed by re-test within 1 week of receiving the test result. The re-test result will be used if the first test is not confirmed.

HBsAg and HBV DNA are collected for primary and secondary efficacy endpoints as per the SoA (see Section 1.3). Details of sample collection can be found in the SRM.

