## 4.8. Changes to Protocol Defined Analyses

Changes from the originally planned statistical analysis specified in the protocol are detailed in [Table 1](#).

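### In the post-treatment windows the SAP's worst-value rule overrides the protocol's HBsAg re-test rule, so one unconfirmed value makes a sustained responder a Non-Responder

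*SAP*

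**What the plan says.** Protocol 8.1 (Efficacy Assessments) sets a confirmation step: "Any HBsAg greater than LLOQ after achieving HBsAg seroclearance needs to be confirmed by re-test within 1 week of receiving the test result". It then says which result counts: "The re-test result will be used if the first test is not confirmed". The same section covers the data for both levels of endpoint: "HBsAg and HBV DNA are collected for primary and secondary efficacy endpoints as per the SoA".

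SAP 6.2.5 defines the analysis windows for sustained HBsAg response and sustained virologic response, after planned and after actual end of treatment. For all of them, "all values including unscheduled visit results will be considered". Selection within a window then depends on the window:

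- End of '836 Treatment (Days 64-98 planned): "The latest available assessment in the window will be selected".
- Each Post '836 window (Days 99-154, 155-210 and 211-266 planned; X+21 to X+188 in three windows for actual, where X is the target day of the last dose): "Worst non-missing value in the analysis window will be selected". The ranking is explicit: "Worst value is defined in the order of: highest actual value, then <LLOQ, and then TND".

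Under SAP 4.3.1.1 and 4.3.1.2, a participant who is not below LLOQ for the 24 weeks is a Non-Responder. SAP 4.8 opens with "Changes from the originally planned statistical analysis specified in the protocol are detailed in" Table 1, and that table lists only the time-to-maximum-ALT analyses. The SAP text mentions no re-test or confirmation step.

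**The concern.** The protocol lets a negative re-test replace an unconfirmed positive. The SAP puts both results into the pool and ranks any quantifiable value above a result below LLOQ, so the negative re-test can never prevail in a Post '836 window. The two documents therefore classify the same participant differently, and the SAP's error runs only downward.

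At stake are four percentages that the SAP presents under its key secondary heading: the planned and actual versions of sustained HBsAg response and of sustained virologic response. In a study of about 20 participants, one reclassified participant is a visible change.

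**Working it through.** No figure in either document depends on this rule, so there is no stated value to reproduce. The check is a classification, followed by a count of exposed tests and an illustration of size.

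**1. One participant under each rule.** Inputs: LLOQ 0.05 IU/mL (SAP 4.1.1) and the planned windows (SAP 6.2.5). Suppose all values are below LLOQ except 0.06 IU/mL on Day 190, with a re-test below LLOQ on Day 197. There are no missing windows and no PEG-interferon or other immunomodulator.

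| Rule | Value used in Days 155-210 | Class |
|---|---|---|
| Protocol 8.1 | re-test, below LLOQ | Responder |
| SAP 6.2.5 | 0.06 (highest) | Non-Responder |

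The same split occurs for a single unconfirmed value on Day 106, 162 or 246. The re-test date does not matter here: even if the re-test fell in the next window, the SAP would keep the first value in its own window. If the re-test confirms the value, both rules give Non-Responder.

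**2. The end-of-treatment window.** The latest value is used. A Day 92 value re-tested on Day 97 gives Responder under both rules. A Day 92 value re-tested on Day 102 does not: Day 92 remains the latest value in Days 64-98, so the SAP gives Non-Responder and the protocol gives Responder.

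**3. Do other SAP sections resolve it?**
- SAP 6.2.4 leaves unscheduled visits unmapped unless otherwise specified, and 6.2.5 specifies otherwise.
- SAP 6.2.6 queries the site about multiple assessments on a scheduled visit. Its closest-to-target hierarchy concerns Early Termination visits and summary statistics. Neither restores the re-test rule.
- Protocol 9.4.4 leaves the post-treatment analysis windows to the analysis plan. That does not extend to which of two results is valid.

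**4. Exposed tests.** HBsAg days from the schedule of activities, counted within the Post '836 windows with every visit attended:

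| Anchor | Study days covered | Scheduled HBsAg days | Count |
|---|---|---|---|
| Planned, or actual with X=78 | 99-266 | 106, 134, 162, 190, 218, 246 | 6 |
| Actual, X=57 | 78-245 | 78, 85, 92, 106, 134, 162, 190, 218 | 8 |
| Actual, X=29 | 50-217 | 50, 57, 64, 71, 78, 85, 92, 106, 134, 162, 190 | 11 |

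**5. Size.** One participant is 100/20 = 5.0 points, or 100/24 = 4.2 points at the maximum enrolment. The documents give no rate q of unconfirmed values per test. With q assumed and tests independent, the probability of losing a true sustained responder is 1-(1-q)^k under the SAP over k tests. With re-testing it is 1-(1-q²)^6 over six tests, because both results must be falsely above LLOQ.

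| q (assumed) | SAP, k=6 | SAP, k=8 | Re-test rule, k=6 |
|---|---|---|---|
| 1% | 5.9% | 7.7% | 0.06% |
| 2% | 11.4% | 14.9% | 0.24% |
| 5% | 26.5% | 33.7% | 1.5% |

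Take an illustrative 5 of 20 true sustained responders (25%) and six tests. The expected fall in the reported percentage is 25 × (0.0585, 0.1142, 0.2649) = 1.5, 2.9 and 6.6 points against the truth. Against the protocol rule it is 25 × (0.0585-0.0006, 0.1142-0.0024, 0.2649-0.0149) = 1.4, 2.8 and 6.3 points.

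**The case against.** The strongest reply is that the rules can run in sequence: Protocol 8.1 first settles the valid result, and SAP 6.2.5 then takes the worst of the valid results. On that reading the SAP is silent rather than contradictory. But the SAP does not state that order. It says that all values are considered and ranks the highest actual value first. A programmer following it literally keeps the unconfirmed value.

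A second reply is that Protocol 8.1 does not say whether a re-test is a new draw or a repeat assay of the same sample. Protocol 7.1.1, by contrast, asks explicitly for new blood. If it is a repeat assay, both results belong to one scheduled visit and the site query in SAP 6.2.6 might settle the matter. That would narrow the cases, but it is one possible reading and the SAP does not connect the query to the re-test.

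Several limits do stand:
- Seroclearance is not defined in either document, so the trigger for the re-test is open to interpretation.
- The documents give no laboratory turnaround time, so the re-test dates in the examples are illustrative.
- The count of 11 for X=29 is a ceiling, because Protocol 7.1 allows a reduced visit schedule after stopping treatment.
- The per-test rates, their independence and the 5 of 20 are assumptions; only the 5 points per participant follows from the documents.
- A worst-value rule is conservative in an open-label single-arm study and may be what the sponsor wants. That would justify choosing it, but it would still be an undeclared departure from the protocol.
- The Output and Programming Specification is not available and could contain a substitution step. The SAP refers to it for other matters but not for this one, and a responder definition belongs in the SAP.

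**Conclusion.** The concern holds. Followed as written, SAP 6.2.5 reverses the protocol's rule for an unconfirmed HBsAg value in every Post '836 window, and in the end-of-treatment window when a Day 92 value is re-tested after Day 98. The effect is 5 points downward per affected participant at N=20. How many would be affected cannot be known from the documents; the loss probabilities rest on the assumed rates and on independence. Exposure rises with earlier discontinuation, so the actual-end versions can be hit harder.

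The consequence is bounded. These are secondary endpoints reported as percentages without testing. The primary endpoint, its posterior probability and the sample size do not change. The protocol's re-test rule covers HBsAg only, so an isolated HBV DNA value is not part of the conflict. This should be fixed before the analysis is run.

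**What to change.** Add to SAP 6.2.5, for the planned and actual windows alike: *Before window selection, an HBsAg value above LLOQ after seroclearance that is not confirmed by the Protocol 8.1 re-test is replaced by the re-test result, which keeps the date of the sample it replaces. A quantifiable value with no re-test stands as observed. The worst-value or latest-value rule is then applied.* Keeping the first sample's date settles the Day 92 case. The treatment of a value with no re-test is a proposal, since Protocol 8.1 does not address it. The same text should say what counts as seroclearance and whether a re-test is a new sample.

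If the sponsor prefers the stricter rule, list it in SAP 4.8 as a departure from Protocol 8.1 and report the protocol rule as a sensitivity analysis.

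The cost is a short SAP insertion and a derivation flag linking each re-test to its first result; the re-tests are already required. The trade-off is that only values above LLOQ are re-tested, so the protocol rule favours response and could hide genuine low-level reappearance. Reporting how many participants are classified differently by the two rules would make that visible.
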